7.4 Diet, Fluid, Activity Control

The principal investigator, the coinvestigators, and the study collaborators are to explain, and give instructions on, the following before the start of the study or during the study, as well as to check to see if the subjects keep to the instructions at the time of their scheduled visits.

- Every subject should keep to the scheduled visits, seek medical consultation, and undergo predetermined laboratory.
- The subject should ensure that all study medications are swallowed with approximately 240 mL water according to the administration, and dosing schedule. Subjects should be instructed according to Section 8.1.3.1 (Missed Doses) and 9.2 (Compliance). Details of any missed or forgotten doses should be reported to the Investigator or designee at the subsequent study visit.
- The subject should store all medications in a cool, dry, safe place which is out of reach of children and to bring all study supplies (empty / used / unused drug packets and diaries alike) to each study visit.

- The subject should record his/her nighttime (during sleep) subjective symptoms and the previous daytime subjective symptoms in his/her subject diary upon rising in the morning on a daily basis. The subject should also record the use of rescue medication since the start of the Screening Period as well as his/her study medication compliance status during the Treatment Phase.
- The subject will be required to fast for at least 8 hours before each visit at which fasted blood tests will be drawn and/or endoscopy will be performed, after the ICF is signed. Fasting is defined as no food or nutritional drinks for 8 hours before the blood draw. Water is allowed. Any medication that needs to be taken with food and any study medications should be held until after the fasting blood has been drawn and/or the endoscopy has been performed. Medication that does not need to be taken with food should be continued. The investigator must instruct the subject accordingly prior to visits in which serum gastrin is measured and endoscopy is performed.
- After the first dose of study drug during the Healing Period and the Maintenance Period, the subject should present to the clinic in the morning as scheduled.

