8.1.3 Dose and Regimen

All subjects with EE confirmed by endoscopy at Screening will be assigned to 60 mg dexlansoprazole or 30 mg lansoprazole capsules QD for 8 weeks of treatment. At the Week 8 Visit, all EE subjects will have an endoscopy. EE subjects who have healed will be randomized to dexlansoprazole 30 mg capsules or placebo for 6 months to assess maintenance of healed EE.

The number of cards subjects will receive at each visit is outlined in [Table 8.c](#).

Table 8.c Study Medication Dispensed at Each Visit

Study Visits	Number of 7-Day Cards Dispensed at #Each Visit
Day -1/Visit 2	5 cards of Dexlansoprazole 60 mg or Lansoprazole 30 mg capsules
Week 4/Visit 3	5 cards of Dexlansoprazole 60 mg or Lansoprazole 30 mg capsules
Week 8/Visit 4	5 cards of Dexlansoprazole 30 mg capsules or Placebo capsules
Month 1/Visit 5	9 cards of Dexlansoprazole 30 mg capsules or Placebo capsules
Month 3/Visit 6	13 cards of Dexlansoprazole 30 mg capsules or Placebo capsules

All subjects will self-administer 1 capsule of blinded study medication QD at approximately the same time each morning. The last dose of study medication is taken with a sip of water on the morning of their visit (Visits 3, 4, 5, 6 and 7).

Table 8.d Study Medication Supplies

Investigational Product	Formulation	Dosage	Mode of Administration	Manufacturer and Location
Dexlansoprazole	30 mg capsule	30 mg QD AM	Oral	Takeda Pharmaceutical Company Ltd
Dexlansoprazole	60 mg capsule	60 mg QD AM	Oral	Takeda Pharmaceutical Company Ltd
Lansoprazole	30 mg capsule	30 mg QD AM	Oral	Tianjin Takeda Pharmaceuticals Company Ltd
Placebo	0 mg capsule	0 mg QD AM	Oral	Fisher Clinical Services

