9.3.3 Healing Period

9.3.3.1 Day 1

- Begin study medication.
- Complete daily diary.

9.3.3.2 *Week 4 Visit (± 3 Days)*

Procedures to be completed at Week 4 Visit include:

- Physical examination.
- GERD symptoms investigator assessment.
- Vital signs.
- Weight.
- AE assessment.
- Concomitant medication(s).
- Clinical laboratory tests (subjects should be fasting for a minimum of 8 hours prior to all labs) to include:
 - Chemistry panel and hematology.
 - Urine hCG.
 - Urinalysis.
- Daily diary review/dispense new diary pages.
- Dispense study medication via IWRS.
- Return of study medication.
- Study drug compliance and accountability.

9.3.3.3 *Week 8/Final Visit (± 3 Days)*

Procedures to be completed at Week 8/Final Visit include:

- Physical examination.
- GERD symptoms investigator assessment.
- Vital signs.
- Weight.
- AE assessment.
- Concomitant medication(s).
- Clinical laboratory tests (subjects should be fasting for a minimum of 8 hours prior to all labs) to include:
 - Chemistry panel and hematology.
 - Serum and urine hCG.
 - Urinalysis.

- Fasting gastrin.
- Daily diary review.
- Return of all study medication for healing period and instruct the subject NOT to take them anymore if the medication is not returned for any special reason(s).
- Study drug compliance and accountability.
- ECG.
- Endoscopy.

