Appendix A Schedule of Study Procedures

	Screening Period		Healing Period			Maintenance Period			Unscheduled Visit	Follow-up Phone Call (c)
	Screening	Study Day -1 Baseline	Study Day 1	Week 4 (a)	Week 8 (a)/ Final Visit	Study Month 1	Study Month 3	Month 6 (b) Final Visit		
Study Day/Week/Month:	Day -21 to -2	Day -1	Day 1	Week 4	Week 8	Month 1	Month 3	Month 6		Last dose +5 to 10 days
Visit Windows (Days):				±3	±3	±7	±7	±7		
Visit Number:	1	2		3	4	5	6	7		8
Informed consent	X									
Demographics/medical/social history	X									
Medication history	X									
Physical examination	X	X		X	X	X	X	X	X	
Concurrent medical conditions	X									
Vital signs, body weight and height	X(d)	X		X	X	X	X	X	X	
ECG	X				X			X	X	
Endoscopy	X (e)				X	X (n)	X(o)	X (n)	X(o)	
H. Pylori serology	X									
Clinical laboratory tests (j)	X (e)			X (f)	X (f)	X (f)	X (f)	X (f)		
Hepatitis panel (j)	X (e)									
Fasting serum gastrin (f)		X			X			X	X	
Urine pregnancy test (k)	X	X		X	X	X	X	X		
Serum hCG (k)	X	X			X			X		
Serum FSH	X(g)									
Guidance on avoidance of pregnancy and ova and sperm donation	X	X		X	X	X	X	X		
IWRS randomization		X			X (m)					

Footnotes are on last table page.

CONFIDENTIAL

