Appendix A Schedule of Study Procedures (continued)

	Screening Period		Healing Period			Maintenance Period			Unscheduled Visit	Follow-up Phone Call (c)
	Screening	Study Day -1 Baseline	Study Day 1	Week 4 (a)	Week 8 (a)/ Final Visit	Study Month 1	Study Month 3	Month 6 (b) Final Visit		
Study Day/Week/Month:	Day -21 to -2	Day -1	Day 1	Week 4	Week 8	Month 1	Month 3	Month 6		Last dose +5 to 10 days
Visit Windows (Days):				±3	±3	±7	±7	±7		
Visit Number:	1	2		3	4	5	6	7		8
First day of study drug			X (l)		X (m)					
Concomitant medications	X	X		X	X	X	X	X	X	
AEs assessment	X	X		X	X	X	X	X	X	X
GERD symptoms assessment (p)		X		X	X	X	X	X	X	
Daily diary review/dispense (h)	---X---	X---	X---	X---	X---	X---	X---	X---		▶
Dispense study drug via IWRS		X (i)		X	X (m)	X(q)	X(q)			
Drug return/accountability				X	X	X	X	X		

Footnotes are on last table page.

- (a) Subjects who prematurely discontinue from the Healing Period should undergo Week 8 / Final Visit procedures no later than 5 days after the last dose of study drug.
- (b) Subjects who prematurely discontinue from the Maintenance Period should undergo Month 6 / Final Visit procedures no later than 5 days after the last dose of study drug.
- (c) Follow-up phone call will occur for all subjects from 5 to 10 days after their last dose of study medication.
- (d) Height is measured only at Screening.
- (e) The screening clinical laboratory tests, hepatitis panel, and endoscopy must be performed within 14 days prior to randomization. Any reliable, documented results available from an endoscopy performed in a routine clinical setting (before signing of informed consent) in the same institution will be accepted instead, given the invasive nature of the procedure.
- (f) Except for Visit 1 (Screening Days -21 to -2), subjects should be fasting for a minimum of 8 hours prior to the specimen collection. During the study drug treatment period, subjects should be instructed to take their dose of study medication on the morning of their visit with a sip of water before specimen collection occurs. Breakfast should be eaten only after specimen collection.
- (g) Only if menopause is suspected.
- (h) Subjects should complete the diary every morning (for nighttime symptoms) and every evening (for daytime symptoms). The diary will be dispensed at Screening and reviewed/dispensed at corresponding subsequent visits.

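### Protocol Section 7.4 and Appendix A footnote (f) give opposite orders for study drug and fasting blood, so on-treatment gastrin and laboratory samples can be taken under two dosing conditions

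*Protocol*

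**What the plan says.** Three parts of the current protocol deal with the study dose on a visit morning.

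- **Section 7.4** requires an 8-hour fast before visits with fasted blood tests or endoscopy, and says that "any study medications should be held until after the fasting blood has been drawn and/or the endoscopy has been performed". It adds: "The investigator must instruct the subject accordingly prior to visits in which serum gastrin is measured and endoscopy is performed".
- **Appendix A, footnote (f)** says that during treatment subjects should "take their dose of study medication on the morning of their visit with a sip of water before specimen collection occurs". The footnote is attached to the fasting gastrin row and to the clinical laboratory entries at Week 4, Week 8 and Months 1, 3 and 6. The endoscopy row does not carry it.
- **Section 8.1.3** says: "The last dose of study medication is taken with a sip of water on the morning of their visit", and lists Visits 3 to 7. It does not place the dose before or after any procedure.

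Two neighbouring texts bear on the same act. Section 7.4 says that "all study medications are swallowed with approximately 240 mL water", while Section 8.1.3 and footnote (f) speak of a sip. At Week 8, Section 9.3.3 lists: "Return of all study medication for healing period and instruct the subject NOT to take them anymore", the second part applying to capsules that were not handed back. Appendix A footnote (m) times the first Maintenance dose about 24 hours after the last Healing dose.

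SAP Section 7.11.2 summarizes gastrin and other laboratory values descriptively, as change from Baseline in the Healing Period and change from Week 8 in the Maintenance Period. It also gives the percentages of subjects with gastrin at or above 200 and 400 pg/mL. It has no rule on the time between dose and sample.

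**The concern.** Section 7.4 is operative text: site staff must explain it to subjects and check that they keep to it. Appendix A is the schedule from which sites run visits. Section 14.2 tells investigators not to deviate from the protocol, yet at a fasting visit during treatment, obeying either passage breaches the other. Which condition a sample is drawn under would then depend on which passage a site was trained on.

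What is at stake is the description of safety, mainly gastrin. Section 9.1.10 says that gastrin is sampled to learn how large its rise is. Gastrin results are blinded to investigators and the medical monitor, so neither would see a site pattern while the study runs. The Week 8 value serves twice, as the last Healing value and as the Maintenance baseline (Protocol Section 13.1.4, SAP Section 7.1.1), so an inconsistency there can enter both change scores.

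**Working it through.** This is a textual contradiction, so the check is to set the passages side by side and see whether any reading satisfies all of them. The only arithmetic is a count of planned samples and one dosing interval.

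| Source | Dose relative to fasting blood | Dose relative to endoscopy | Water |
|---|---|---|---|
| Section 7.4 | after | after | about 240 mL (general instruction) |
| Appendix A (f) | before | not stated | a sip |
| Section 8.1.3 | visit morning, order not stated | visit morning, order not stated | a sip |

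**1. Fasting blood.** Section 7.4 and footnote (f) are opposites. Section 8.1.3 does not settle the matter, because a dose on the visit morning can come before or after the draw.

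**2. Does a narrow reading of Section 7.4 help?** Suppose that its hold applies only to the visits its closing sentence singles out, those with gastrin and endoscopy. Week 8 and Month 6 have both, and footnote (f) is attached to the gastrin row itself. The conflict therefore remains at the two scheduled on-treatment gastrin visits. On the plain reading it covers Visits 3 to 7.

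**3. Endoscopy.** Section 7.4 says to hold the dose. No passage says to take it before endoscopy. A conflict arises only by inference, at visits where blood and endoscopy fall on the same morning (Visits 4, 5 and 7, and optionally 6).

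**4. Samples exposed.** The Day -1 gastrin sample precedes the first dose and is unaffected. Planned numbers are 225 + 225 = 450 subjects in Healing and 150 + 150 = 300 in Maintenance. Ignoring dropout, which makes these ceilings:

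- Scheduled on-treatment gastrin: 450 (Week 8) + 300 (Month 6) = 750 samples. Of these, 150 at Month 6 are on placebo, where capsule timing carries no drug, leaving 750 − 150 = 600.
- Fasting laboratory visits: 450 × 2 (Visits 3, 4) + 300 × 3 (Visits 5, 6, 7) = 1,800.

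Unscheduled visits, where gastrin is also listed, come on top.

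**5. Week 8 handover.** If the Week 8 dose is taken that morning, before or after the draw, the first Maintenance dose next morning is about 24 hours later, as footnote (m) states. If a held dose were then not taken because the Healing supply had been returned, the last Healing dose would be the previous morning's and the interval would be 24 + 24 = 48 hours. The text does not direct this. It does show that the visit-day instruction, the drug return and footnote (m) have to be worded together.

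**6. Can the mix be separated afterwards?** The documents describe no record of dose time against sample time. The diary questions in Appendix H cover heartburn and rescue medication only.

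**The case against.** The strongest reply is that the consequence is small. Section 4.1 describes gastrin rising over the first 3 months of treatment, generally stabilizing, and returning to Baseline within 7 days of the last dose. These are changes over days to months, and nothing suggests that the order of events on one morning matters. The plan also tolerates far wider gaps: early-termination procedures up to 5 days after the last dose, and gastrin in the analysis up to 7 days after the last day of study drug (SAP Section 7.1.1). Both blinded arms receive the same instructions, and gastrin is only described. Sampling details are left to a laboratory manual that is not available here and may settle the point in practice.

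Most of this stands, and it limits the size of the concern. It does not remove the contradiction: a manual does not amend the protocol, and a site complying with one passage still breaches the other.

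The reply is also right about several stronger readings that a reader might infer:

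- *Section 8.1.3 also requires dosing before sampling.* It gives no order. Its sip of water echoes footnote (f), but that is support by implication.
- *Subjects are told to dose before endoscopy.* No passage says so.
- *The two water volumes contradict each other.* They can be read as a general daily rule beside a visit-morning rule.
- *It is open whether the Week 8 dose is taken at all.* Section 8.1.3 lists Visit 4, and SAP Section 7.1.1 treats the visit day as the last dosing day. What is open is the order within the morning and how a held dose fits with the drug return.

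**Conclusion.** For fasting blood, Section 7.4 and Appendix A footnote (f) cannot both be followed, and no passage gives either precedence. On-treatment gastrin at Week 8, Month 6 and unscheduled visits, and fasting laboratory samples at Visits 3 to 7, can therefore be drawn under two dosing conditions. I say can, not will: it depends on which passage each site follows.

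The expected harm is added variability and site-to-site inconsistency in descriptive safety summaries, including the percentages at the two gastrin thresholds. Its size cannot be derived, because the documents give no pre-dose against post-dose gastrin difference.

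A reader might go on to infer bias between arms, or a threat to the healing result. The documents support neither. Both arms share the instructions, and nothing links the timing of one morning's dose to endoscopic healing or to the noninferiority conclusion. Nor does the problem reach about 450 subjects at every visit; Visits 5 to 7 involve the roughly 300 expected in Maintenance.

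The contradiction itself rests on current protocol text and needs no numerical assumption. The sample counts assume the planned numbers with no dropout.

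**What to change.** Reconcile Section 7.4, Section 8.1.3 and Appendix A footnote (f) into one visit-day instruction that states the order of study dose, fasting blood and endoscopy. Which order applies is for the sponsor to decide. Word it so that it agrees with the Week 8 drug return in Section 9.3.3 and the 24-hour timing in footnote (m), and say at the same time which water instruction applies on a visit morning.

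From then on, record on the eCRF whether the dose was taken before or after sampling, ideally with both times, so that gastrin can be described by dosing status. For visits already done, describe dosing status only where source documents show it; new eCRF fields cannot by themselves recover times that nobody wrote down.

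The cost is a protocol clarification, a memo to sites and one or two eCRF fields. No endpoint, sample size or planned test changes.

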7.5 Criteria for Discontinuation or Withdrawal of a Subject

The primary reason for discontinuation or withdrawal of the subject from the study or study drug should be recorded in the electronic case report form (eCRF) using the following categories. For screen failure subjects, refer to Section 9.1.13.

1. Pretreatment event (PTE) or adverse event (AE). The subject has experienced a PTE or AE that requires early termination because continued participation imposes an unacceptable risk to the subject's health or the subject is unwilling to continue because of the PTE or AE.

- Liver Function Test Abnormalities
 - Study medication should be discontinued immediately with appropriate clinical follow-up (including repeat laboratory tests, until a subject’s laboratory profile has returned to normal/baseline status, see Section 9.1.10), if the following circumstances occur at any time during study medication treatment:
 - ALT or AST $>8\times$ ULN, or
 - ALT or AST $>5\times$ ULN and persists for more than 2 weeks, or
 - ALT or AST $>3\times$ ULN in conjunction with elevated total bilirubin $>2\times$ ULN or international normalized ratio (INR) >1.5 , or
 - ALT or AST $>3\times$ ULN with appearance of fatigue, nausea, vomiting, right upper quadrant pain or tenderness, fever, rash, and/or eosinophilia ($>5\%$).
- 2. Significant protocol deviation. The discovery post-randomization that the subject failed to meet protocol entry criteria or did not adhere to protocol requirements, and continued participation poses an unacceptable risk to the subject’s health.
- 3. Relapse of EE during the Maintenance Period.
- 4. Lost to follow-up. The subject did not return to the clinic and attempts to contact the subject were unsuccessful. Attempts to contact the subject must be documented in the subject’s source documents.
- 5. Voluntary withdrawal. The subject (or subject’s legally acceptable representative) wishes to withdraw from the study. The reason for withdrawal, if provided, should be recorded in the eCRF.

Note: All attempts should be made to determine the underlying reason for the withdrawal and, where possible, the primary underlying reason should be recorded (ie, withdrawal due to an AE or lack of efficacy should not be recorded in the “voluntary withdrawal” category).
- 6. Study termination. The sponsor, IRB, IEC, or regulatory agency terminates the study.
- 7. Pregnancy. The subject is found to be pregnant.

Note: If the subject is found to be pregnant, the subject must be withdrawn immediately. The procedure is described in Section 9.1.12.
- 8. Lack of efficacy. The investigator has determined that the subject is not benefiting from investigational treatment and continued participation would pose an unacceptable risk to the subject.
- 9. Other.

Note: The specific reasons should be recorded in the “specify” field of the eCRF, for example: noncompliance.

7.6 Procedures for Discontinuation or Withdrawal of a Subject

The investigator may terminate a subject's study participation at any time during the study when the subject meets the study termination criteria described in Section 7.5. In addition, a subject may discontinue his or her participation without giving a reason at any time during the study. Should a subject's participation be discontinued, the primary criterion for termination must be recorded. In addition, efforts should be made to perform all procedures scheduled for the Early Termination Visit. Discontinued or withdrawn subjects will not be replaced.

8.0 CLINICAL TRIAL MATERIAL MANAGEMENT

This section contains information regarding all medication and materials provided directly by the sponsor, and/or sourced by other means, that are required by the study protocol, including important sections describing the management of clinical trial material.

8.1 Study Medication and Materials

Once a subject meets all eligibility criteria, the site will randomize the subject via the IWRS, which will assign a unique study drug identification number. The subject will be randomized into the Healing Period in a 1:1 ratio into 1 of 2 treatment groups:

- Dexlansoprazole 60 mg capsules.
- Lansoprazole 30 mg capsules.

At Week 8 of the Treatment Period, if the subject is healed per the endoscopy, the subject will be randomized into the Maintenance Period in a 1:1 ratio to 1 of 2 treatment groups:

- Dexlansoprazole 30 mg capsules.
- Placebo capsules.

Randomization will be stratified by baseline endoscopic findings (grades A/B or C/D) for both the Healing and Maintenance Periods.

8.1.1 Dosage Form, Manufacturing, Packaging, and Labeling

In this protocol, the term study medication refers to all or any of the drugs defined below.

During the 8-week Healing Period and for the 6-month Maintenance Period, blinded study drug will be provided according to [Table 8.a](#).

Table 8.a Study Drugs

Study Drugs	Dosage Strength/Dosage Form	Manufacturer
Dexlansoprazole	30 and 60 mg capsules	Takeda Pharmaceutical Company Ltd.
Lansoprazole	30 mg capsules	Tianjin Takeda Pharmaceuticals Company Ltd.
Placebo	capsules (dose is not applicable)	Fisher Clinical Services

The study sites will be supplied with study medication that is blinded via overencapsulation (OE) of dexlansoprazole 60 mg capsules and lansoprazole 30 mg capsules for subjects in the 8-week Healing Period. Sites enrolling subjects in the Maintenance Period will also be supplied with OE dexlansoprazole 30 mg and placebo. The study drugs will be foil/foil blistered and packaged in 7-day child resistant blister cards containing 7 capsules. Each card will have a single-panel multilingual label that will contain, but will not be limited to: protocol number, medication identification (ID) number, name and strength of the product, quantity of dosage unit, directions for use, storage conditions, country specific regulatory caution statement, and name and address of the sponsor. The matching placebo capsules will be manufactured by Fisher Clinical Services. The

study medication is overencapsulated, foil/foil blistered, packaged, labeled and distributed by Fisher Clinical Services.

